ENDPOINTS:

Primary Endpoint

- One point decrease from baseline in target lesion Global PG (GPG) Severity Score at Week 16

Secondary Endpoints

- Complete re-epithelization of PG lesions (GPG Severity Score of 0) at visits 3, 4, 5, 6, 7, 8, and 9.
- Absolute change from baseline in patient-reported pain severity (Pain-VAS) at visits 3, 4, 5, 6, 7, 8, and 9 and at complete re-epithelization of ulcer.
- Absolute change in quality of life (DLQI) from baseline at visits 3, 4, 5, 6, 7, 8, and 9 and at complete re-epithelization of ulcer.
- Recurrence of PG lesions after complete re-epithelization (GPG score 0) of all lesions and spesolimab cessation

- Time to worsening (1 or more GPG point increase) of target PG lesion from spesolimab cessation

STUDY DESIGN OVERVIEW:

This study is a prospective, proof-of-concept, open label clinical trial. The study will take place at Icahn School of Medicine at Mount Sinai.

The study will screen up to 25 subjects in order to enroll a total of up to 20 patients with at least one clinically measurable ulcerative PG lesion. Subjects will receive 900 mg of spesolimab intravenously (IV) over 90 minutes at a frequency of every 4 weeks until Week 28 with the following exceptions:

- At the Week 8 visit, subjects who do not show any improvement, show only minimal improvement, or those that begin to lose their initial improvement response (decrease in pain or wound drainage), may be switched to a dosing frequency of every 3 weeks through Week 26, at the discretion of the investigator. These subjects will still return at Week 16 for an endpoint visit, but will not receive treatment at this visit. Refer to Tables 3 and 4 for schedule of events.

All subjects will be monitored monthly for 4 months subsequent to treatment cessation.

Subjects who reach GPG score 0 at anytime during the study will continue to receive treatments until week 28 (or Week 26 depending on dosing frequency) and will then be monitored for 4 months subsequent to treatment cessation.

Subjects who are experiencing improvement in their PG but who have not reached complete wound healing will continue treatment until Week 28 (or Week 26 for those who were switched to every 3 week dosing), even if primary endpoint has been achieved. These subjects will then be monitored for 4 months subsequent to treatment cessation.

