Subjects who have not improved and not worsened significantly will also continue to receive treatments until week 28 (or Week 26 depending on dosing frequency) and will then be monitored for 4 months subsequent to treatment cessation.

Any subject that experiences significant worsening will be discontinued from the study.

After providing consent, subjects will be assessed for study eligibility during the screening period (within 28 days of baseline). The screening visit includes a review of the subject's past and current medical conditions as well as a review of family history of associated relevant diagnoses such as inflammatory bowel disease, rheumatoid arthritis, and hematological malignancy. Subjects will also be asked to review past surgical history and history of any relevant skin trauma. Subjects will also be asked to report past and current treatment regimens of their PG and their perception of response to each treatment trialed. A limited physical exam will be performed, vitals collected, blood samples collected for safety tests (including screenings for HIV, hepatitis B and C and tuberculosis), and the physician will assess number, location, and severity of PG lesions.

Subjects who meet inclusion criteria for eligibility will undergo Baseline assessments at Week 0, including clinical assessments, review of concomitant medications, limited physical examination, vitals, standardized clinical photography, questionnaires (patient PG questionnaire, pain VAS and DLQI). Blood samples (CBC, CMP, CRP, serum cytokine profiles, pharmacokinetics, Nab, ADA) will be collected to monitor for adverse effects of medication and overall inflammatory response.

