Contraindications to spesolimab treatment include patients with severe or life-threatening hypersensitivity to spesolimab or to any of the excipients in spesolimab¹⁴. In our experience, patients infused with spesolimab exhibited no adverse reactions during or after treatment with no pre-medication required. There is limited data available on the impact of antidrug antibodies on safety and efficacy upon retreatment. Furthermore, it is not known whether spesolimab increases or decreases the efficacy of other medications.

PRIOR TREATMENT:

All relevant treatment received by the subject within 30 days before screening will be recorded.

CONCOMITANT TREATMENT:

Concomitant medications are permitted for the treatment of stable, chronic illness as well as for pyoderma gangrenosum. Concomitant treatments for pyoderma gangrenosum will tapered over spesolimab treatment course as tolerated. Use of such concomitant medication or other medications that may be required throughout the study will be recorded (including the reason for treatment and name, dose, unit, route, and the date of treatment as appropriate) until treatment termination and throughout follow-up period. Patients will be allowed to continue with biologic therapies used to treat comorbidities.

PROHIBITED TREATMENT:

All treatments prohibited by clinician during the screening period are also prohibited throughout the course of the study. No live attenuated vaccinations are permitted throughout the study.

PROCEDURES:

Monitoring of AEs will begin at the time of signing the informed consent form and will be continued throughout the course of the study. All study procedures will be completed at designated times during the study period (see Tables 3 and 4). Subjects will receive 900mg IV spesolimab at a frequency of every 4 weeks through Week 8, at which time, at the discretion of the investigator, dosing frequency may be increased to every 3 weeks. Subjects will continue to dose every 4 or 3 weeks through Week 28 or 26 (depending on

dosing frequency). Subjects will be monitored once a month, for 4 months after treatment cessation. Patients that, in the opinion of the investigator, are benefiting from treatment at week 28 but need more therapy to achieve wound closure may be eligible to continue on treatment (on case-by-case basis) to a maximum of 52 week after discussion with Boehringer Ingelheim trial team.

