Subjects are numbered sequentially. Each subject screened (total of 25 screened) will be assigned a unique screening number for the duration of the study. Subject screening numbers will also become a subjects treatment number if they are enrolled in the study after providing informed consent and meeting inclusion criteria. Subjects who discontinue or withdraw from the study before receiving a treatment assignment code, but re-enroll at a later time must be assigned a new screening number. The investigator must maintain a master log linking the subject number to the subject's name. The investigator must follow all applicable privacy laws in order to protect a subject's privacy and confidentiality.

INVESTIGATIONAL DRUG SUPPLY :

Eligible participants will receive 900 mg intravenous spesolimab starting at Visit 2/week 0/Baseline. All participants will receive a total of 8 or 9 infusions (depending on dosing frequency) through Week 28 or Week 26 (depending on whether the subject's dosing frequency is increased to every 3 weeks at Week 8), unless there is significant worsening. All subjects should be observed for 30 minutes following the infusion at Baseline to assess safety. Select cases will be offered the opportunity to continue treatment through Week 52 on case-by-case basis if the patient would benefit from continued treatment. All subjects who have not been discontinued will be monitored once a month, for 4 months after treatment cessation.

All study medication will be provided by Boehringer Ingelheim, refrigerated and stored between 2-8°C in a secure area. Study drug will be administered to subjects at each study visit in office. The investigative site will account for all study drug dispensed and stored during the study.

STATISTICAL CONSIDERATIONS:

Sample Size

This is a proof-of-concept, open-label trial. Twenty patients will be enrolled in the trial to demonstrate efficacy of spesolimab in a population of patients with moderate-severe, refractory PG. Although there is no formal power calculation, a sample size of n=20 subjects allows 81% power at 2.5% significance for a one-sided binomial test to detect at Week 16 a difference of 36.6% in the proportion of GPG success compared to a constant set to be equal to 10%. The choice of the constant was based on data from a randomized clinical trial for efficacy of infliximab where a group of 17 PG placebo-treated patients showed 6% response at Week 2 (Brooklyn et al.,2006).

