Demographics and Other Baseline Characteristics

Descriptive statistics of demographics and other baseline characteristics of patients will be summarized with mean, median, and standard deviation for quantitative outcomes, and frequency and percentage tables for categorical outcomes.. Other baseline characteristics include sex, age, height, weight, vital signs, duration of PG, history of pathergy or PG trigger (if known), concurrent diagnoses from medical history and indications for concomitant medication, concomitant medication, and previous PG treatments.

Target Lesion Measurement and Digital Image Assessments

Size of target PG lesion will be approximated at each visit by measuring the length, width and depth of the lesion. Target lesion will also be analyzed using Image J software to obtain a more precise surface area of each lesion using digital photographs taken at each visit.

Analysis of Primary Endpoint

We will compare the proportion of patients achieving one-point decrease in target lesion GPG score at Week 16 with a constant p=0.10. Clopper-Pearson 90% confidence interval will be estimated.

Analysis of Secondary Endpoints

- One sided Clopper-Pearson 90% confidence intervals will be estimated for the proportion of patients achieving re-epithelization (GPG Severity Score of 0) at Visits 3, 4, 5, 6, 7, 8, and 9
- We will apply a two-sided paired t-test to evaluate significance of the mean difference of GPG score at Week 16 versus Week 0.
- Mean patient reported scores of pain (Pain VAS) and quality of life (DLQI) at baseline will be compared to those at Week 16 and treatment termination using the student's t- test to compare between subject's pre and post-treatment scores.
- One sided Clopper-Pearson 90% confidence intervals will be estimated for the proportion of patients with recurrence or worsening of PG lesions from point of complete re-epithelization or spesolimab cessation at end of treatment visit (Week 28 or Week 26 depending on dosing frequency).

Interim Analysis

An interim analysis will be performed after the first 10 subjects complete Week 16. We will continue enrollment during this time. Proportion of patients achieving one-point GPG score decrease will be reported. Changes from baseline at Week 16 in the PG lesions (number, size, GPG score) will be evaluated and reported. Enrolled subjects will continue to receive treatments during this time.

Data Transfer and Management

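### No denominator or non-responder rule covers subjects discontinued for worsening before Week 16: the interim cohort and paired Week 16 GPG test omit them, and the primary rate is open to the same upward bias

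*Combined protocol and SAP*

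**What the plan says.** The primary endpoint (Endpoints) is "One point decrease from baseline in target lesion Global PG (GPG) Severity Score at Week 16". Its analysis (Statistical Considerations, Analysis of Primary Endpoint) reads: "We will compare the proportion of patients achieving one-point decrease in target lesion GPG score at Week 16 with a constant p=0.10". The Sample Size section claims that "a sample size of n=20 subjects allows 81% power at 2.5% significance for a one-sided binomial test".

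On removal, the Study Design Overview says: "Any subject that experiences significant worsening will be discontinued from the study". The section on discontinuation and withdrawal again lists significant worsening as a reason for withdrawal. Subjects who neither improve nor worsen significantly stay on treatment.

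Three further provisions matter:

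- Interim Analysis: "An interim analysis will be performed after the first 10 subjects complete Week 16". Enrolment continues, the results are reported, and no decision rule is attached.
- Analysis of Secondary Endpoints: "We will apply a two-sided paired t-test to evaluate significance of the mean difference of GPG score at Week 16 versus Week 0". Pain and DLQI are compared with baseline at Week 16 and at treatment termination.
- Concomitant Treatment: "Concomitant medications are permitted for the treatment of stable, chronic illness as well as for pyoderma gangrenosum". PG treatments are to be tapered as tolerated, and their use is recorded.

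A GPG score is scheduled at the Early Termination visit. The available text does not say whether that score enters any Week 16 analysis. It defines no analysis set, no missing-data or non-responder rule, and no analysis rule for subjects whose PG therapy is started or increased. A few pages were not available, so this absence was checked only in the text at hand.

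**The concern.** A subject discontinued for worsening before Week 16 has failed the primary endpoint and also has no Week 16 score. The outcome itself causes the missing value. An analysis restricted to subjects with a Week 16 score drops failures and keeps every success.

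For the interim and the paired GPG test, this follows from the wording. A subject removed at Week 8, say, cannot be among the first 10 to complete Week 16 and has no Week 16 value to pair with baseline. For the primary rate it depends on a choice that the plan leaves open. With a single arm of 20 and a fixed comparator of 10%, no control group shares the selection, and one step in the critical count can decide the result.

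**Working it through.** **Inputs from the documents.** n=20, null rate 0.10, one-sided 2.5% exact binomial test (Sample Size). The primary-analysis paragraph does not repeat the 2.5% level, so it is carried over here.

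**Step 1: reproduce the plan's figure.** The critical count is the smallest r with P(X≥r | 20, 0.10) ≤ 0.025.
- P(X≥5)=0.0432, too large. P(X≥6)=0.0113. The rule is 6 or more of 20, with type I error 1.1%.
- Power at a response rate of 36.6%: P(X≥6 | 20, 0.366)=0.799, close to the stated 81%. If 36.6% is a difference, the rate is 46.6% and power is 0.959. The stated power therefore fits 36.6% as a rate, and it is used that way below.

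**Step 2: completer analysis under the null.** Assume a share w of all subjects, none of them responders, is removed before Week 16. The documents give no value for w, so a range is shown. The number removed is K ~ Bin(20, w), and m=20−K remain. Responders are 10% of all 20, so the rate among those who remain is 0.10/(1−w). With r_m the exact critical count for m subjects,

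type I error = Σ_k P(K=k) × P(X≥r_m | m, 0.10/(1−w)).

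Here r_m is 6 for m=18 to 20 and 5 for m=12 to 17.

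| Removed (w) | Expected completer rate | Type I error, completers | Type I error, all 20 |
|---|---|---|---|
| 0% | 10.0% | 1.1% | 1.1% |
| 5% | 10.5% | 1.3% | 1.1% |
| 10% | 11.1% | 1.9% | 1.1% |
| 15% | 11.8% | 2.6% | 1.1% |
| 20% | 12.5% | 3.3% | 1.1% |
| 30% | 14.3% | 4.5% | 1.1% |

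**Step 3: one data set, different denominators.** With 5 responders:
- 5/20 = 25%, p=0.0432
- 5/19 = 26%, p=0.0352
- 5/18 = 28%, p=0.0282
- 5/17 = 29%, p=0.0221

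Three removals are the first number that turns this result from fail to pass.

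**Step 4: interim.** Suppose 4 of the first 10 completers respond and 2 subjects dosed before the tenth completer were removed for worsening. The report would show 4/10 = 40%; over all 12 it is 4/12 = 33%.

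**Step 5: power after the fix.** Counting removed subjects as failures leaves power at 0.80 if 36.6% is the rate among all treated. If 36.6% holds only among those who stay, the rate over all 20 is 0.366×(1−w):
- w=10%: 32.9%, power 0.69
- w=20%: 29.3%, power 0.56
- w=30%: 25.6%, power 0.41

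**Step 6: added PG therapy (illustration only).** Suppose the success rate is 10% without added therapy.
- If 10% of subjects add therapy and 30% of them succeed, the overall rate is 0.9×0.10+0.1×0.30=12%, and P(X≥6 | 20, 0.12)=0.026.
- If 20% add therapy and 50% of them succeed, it is 0.8×0.10+0.2×0.50=18%, and the probability is 0.136.

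Both inputs in each case are assumptions; the documents give no rate of use.

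**The case against.** A reader might infer that the Week 16 primary rate is biased upward as planned. The documents do not support that. The primary-analysis text names no denominator, the test is sized on n=20, and nothing says that removed subjects are dropped. With all 20 counted and removals as failures, removal causes no inflation. Nor does the design remove every failure: subjects without improvement who have not worsened significantly stay in, and only removals before Week 16 matter.

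The size is also limited. With 10% removed, the completer test still holds its 2.5% level. Six responders pass at n=20 whatever the denominator, so the 5/17 example sits at the edge. The interim has no stopping rule and spends no alpha, so its bias affects a report only. The treatment-termination comparison of pain and DLQI might include subjects who stop early, though the text does not settle this.

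A second tempting reading is that improvement under added PG therapy will be credited to spesolimab. The plan is to taper such therapy, prohibited medication ends study treatment, and no rate of added use is given. Counting every new or increased therapy as failure is one defensible estimand; a treatment-policy approach is another.

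All of this stands. It makes the primary-rate bias conditional and moves added therapy to a sensitivity analysis. It does not supply the missing denominator or bring removed subjects back into the interim cohort and the paired GPG test.

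**Conclusion.** The concern holds in this form. As written, the interim cohort and the paired Week 16 GPG test leave out subjects removed for worsening before Week 16, as does the Week 16 comparison of pain and DLQI. The primary rate is exposed to the same selection because its denominator and non-responder rule are unstated.

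If completers were used, the type I error would pass 2.5% at about 15% of subjects removed and reach 4.5% at 30%, against 1.1% with all 20 counted. These figures assume that everyone removed is a non-responder, that the true rate over all 20 is 10%, and that the exact one-sided 2.5% test applies. The actual removal rate is unknown, so the size is a range and not an estimate. Since the pass/fail result can turn on the choice, it should be fixed before Week 16 data are examined.

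**What to change.** Add to the Statistical Considerations:

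1. **Primary set.** All subjects given at least one infusion. Discontinuation before Week 16, or a missing Week 16 GPG, counts as non-success. With 20 treated, the rule stays at 6 or more of 20.
2. **Interim.** Report on the first 10 dosed subjects who have reached Week 16 or stopped earlier, with the same non-success rule.
3. **GPG, pain and DLQI change.** Add a sensitivity analysis that uses the Early Termination value, or assigns the worst rank, for subjects removed for worsening. Early Termination values come from a different time point, which is why this is a sensitivity analysis. Confirm that the visit also covers subjects discontinued by the investigator; the discontinuation section names it for those who elect to withdraw.
4. **Added PG therapy.** Add a sensitivity analysis of the primary rate that counts subjects with new or increased PG therapy before Week 16 as non-success. Define which therapies count, since biologics for comorbidities may continue.

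The cost is SAP wording; the visits and GPG scores are already scheduled. The observed rate may be lower. Power may fall too if 36.6% describes only subjects who stay: about 0.69 with 10% removed and 0.56 with 20%, against 0.80. No change to the discontinuation rules is proposed.
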